4.2 CONCOMITANT THERAPY, RESTRICTIONS, AND RESCUE TREATMENT

4.2.1 Rescue medication, emergency procedures, and additional treatment

Rescue medication

Rescue medications to reverse the action of afatinib are not available. There is no specific antidote for overdosage with afatinib. In cases of suspected overdose, afatinib should be withheld and supportive care initiated. If indicated, elimination of unabsorbed afatinib may be achieved by emesis or gastric lavage. Potential adverse events should be treated symptomatically. The current version of the Investigator Brochure (IB) lists the AEs expected

Proprietary confidential information.

© 2019 Boehringer Ingelheim International GmbH or one or more of its affiliated companies. All rights reserved.

This document may not - in full or in part - be passed on, reproduced, published or otherwise used without prior written permission.

with afatinib ([c01617169-04](#)). Common adverse events of treatment with afatinib with specified management recommendations and/or requirements include diarrhoea, stomatitis/mucositis, and rash/acne. To improve tolerability and the probability of clinical benefit, patients should receive prompt and appropriate supportive care at the first signs of symptoms. Suggested treatments for AEs are described in [Appendix 10.1](#). Symptomatic treatments of side effects or tumour -associated symptoms are allowed.

Emergency procedures

Careful assessment of all patients with an acute onset and/or unexplained worsening of pulmonary symptoms (dyspnoea, cough, fever) should be performed to exclude Interstitial Lung Disease (ILD). Trial drug should be paused pending investigation of these symptoms. If interstitial lung disease is diagnosed, trial drug must be permanently discontinued and appropriate treatment instituted as necessary.

4.2.2 Restrictions

4.2.2.1 Restrictions regarding concomitant treatment

In this trial supportive treatments will be defined as the best care available judged by the investigator, according to the institutional standards for each center. Concomitant medications (or therapy) to provide adequate care may be given as clinically necessary.

For symptom control, palliative radiation therapy or total VATS is allowed. After trial enrolment, palliative radiotherapy may be given for bone pain or for other reasons (e.g. bronchial obstruction, skin lesions), provided that the total dose delivered is in a palliative range according to institutional standards. During palliative radiotherapy, trial treatment should be delayed and may be resumed once the patient has recovered from any radiation associated toxicity. If medication is continuously interrupted for more than 14 days, the decision to continue will be made by the investigator following discussion with the sponsor.

All concomitant therapy must be recorded in the patient's chart during the screening and treatment period, starting from the date of signature of informed consent, and ending at the Follow-Up Visit (FU).

In case of major surgery (as judged by the investigator), it is recommended to stop treatment with afatinib around one week prior to the surgery, and to restart treatment after complete wound healing, provided that complete wound healing occurs ≤ 6 weeks.

Additional experimental anti-cancer treatment and/or standard chemo-, immunotherapy, hormone treatment (with the exception of megestrol acetate and use of anti-androgens and/or gonadorelin analogues for treatment of prostate cancer), or radiotherapy (other than palliative radiotherapy for symptom control) is not allowed concomitantly with the administration of trial treatment.

Afatinib is a substrate of the P-gp transporter. Strong inhibitors of P-gp (including: Amiodarone, Azithromycin, Captopril, Carvedilol, Clarithromycin, Conivaptan,

Proprietary confidential information.

© 2019 Boehringer Ingelheim International GmbH or one or more of its affiliated companies. All rights reserved.

This document may not - in full or in part - be passed on, reproduced, published or otherwise used without prior written permission.

Cyclosporine, Diltiazem, Dronedarone, Erythromycin, Felodipine, Itraconazole, Ketoconazole, Lopinavir, Nelfinavir, Ritonavir, Quinidine, Ranolazine, Saquinavir, Tacrolimus, Ticagrelor, Verapamil) if administered prior to afatinib may lead to increased exposure to afatinib and therefore should be used with caution. If P-gp inducers (including: Carbamazepine, Phenytoin, Rifampicin, St John's Wort, Phenobarbital Salt, Tipranavir, Ritonavir) need to be taken, they should be administered simultaneously with or after afatinib. Concomitant treatment with strong inducers of P-gp may decrease exposure to afatinib ([U12-1482-01](#)). As the information on potent inhibitors and inducers of P-glycoprotein may evolve, it is important for the investigator to assess such status on concomitant therapies.

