Afatinib is a substrate of the P-glycoprotein (P-gp) transporter. Concomitant administration of the potent P-gp inhibitor ritonavir did not relevantly change the exposure to 40 mg afatinib when taken simultaneously with or 6 h after afatinib but increased the bioavailability of afatinib (single dose of 20 mg) by 48% and 39% for AUC_{0-∞} and C_{max} when given 1 h before afatinib, respectively. Pretreatment with the potent P-gp inducer rifampicin decreased the plasma exposure of 40 mg afatinib by 34 % afatinib (AUC_{0-∞}) and 22 % (C_{max}),

Proprietary confidential information.

© 2019 Boehringer Ingelheim International GmbH or one or more of its affiliated companies. All rights reserved.

This document may not - in full or in part - be passed on, reproduced, published or otherwise used without prior written permission.

respectively. If P-gp inhibitors need to be taken, they should be administered simultaneously with afatinib (see [Section 4.2.2.1](#)) [[U12-1170-01](#)].

In pre-clinical trials s afatinib is not irritant to intact skin but an ocular irritant. Afatinib is mutagenic in a single bacteria strain, but did not show genotoxic potential in vivo when tested up to overt toxic/lethal doses. Studies on embryo-foetal development in rats and rabbits up to life-threatening doses have revealed no indication of teratogenicity.

Two phase I open label dose-escalation trials ([U07-3128-02](#), [U08-1023-03](#)) each determined a Maximum Tolerated Dose (MTD) with continuous dosing of afatinib as 40 mg and 50 mg daily, respectively. Both daily doses (40mg and 50mg) have been used in

Phase II and Phase III trials depending on the patient population evaluated. Adverse Events (AEs) observed with afatinib are consistent with those reported for EGFR and dual EGFR/ Human Epidermal Growth Factor Receptor 2 (HER2) inhibitors. The most common AEs in Afatinib monotherapy trials were associated with gastrointestinal disorders (including diarrhoea, and stomatitis), skin and subcutaneous tissue disorders (rash/acne, dry skin, pruritus), nail effects, fatigue and decreased appetite.-Early and proactive management of diarrhoea, skin rash, mucositis and stomatitis together with treatment interruptions and dose reductions is recommended in line with recent guidelines in the management of common toxicities of EGFR and EGFR/HER2 TKIs and monoclonal antibodies ([R07-4077](#), [P07-11507](#), [R07-4078](#), [R11-0826](#)).

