4.1.1 Identity of BI investigational product and comparator product

Substance (INN):	afatinib (BIBW 2992)
Pharmaceutical form:	Film-coated tablets
Source:	Boehringer Ingelheim Pharma GmbH & Co. KG
Unit strength:	40, 30, and 20 mg film-coated tablets (the dose of afatinib in the film-coated tablets is related to the free base equivalent of afatinib)
Daily dose:	40 mg with an option to reduce the dose based on individual tolerability (see Section 4.1.4.1).
Duration of use:	Continuous daily dosing, one cycle consists of 28 days. Patients are eligible for repeated treatment cycles in the absence of symptomatic disease progression or other trial withdrawal criteria.
Route of administration:	Oral (swallowed)
Posology:	Once daily
Excipients	Core Tablet: Lactose monohydrate, Microcrystalline cellulose, Colloidal silicon dioxide, Crospovidone, and Magnesium stearate. Film-coat: Hypromellose 2910, Polyethylene glycol 400, Titanium dioxide, Talc, FD&C Blue No. 2 11-14% (may not be included in 20 mg tablet), and Polysorbate 80.

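### The concomitant-treatment section (4.2.2.1) attaches the P-gp timing rule to inducers, whereas Section 1.2 gives it for inhibitors and refers to 4.2.2.1; this is probably a word slip and should be corrected

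*Protocol*

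**What the plan says.** Protocol Section 1.2 (Drug profile) summarises the interaction data and draws a dosing rule from them: "If P-gp inhibitors need to be taken, they should be administered simultaneously with afatinib". It then refers the reader to Section 4.2.2.1.

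Section 4.2.2.1 (Restrictions regarding concomitant treatment) deals with the two drug classes in turn.

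- **Inhibitors.** It names 22 strong inhibitors and says that these, "if administered prior to afatinib may lead to increased exposure to afatinib and therefore should be used with caution". It does not say when they should be taken.
- **Inducers.** The next sentence begins "If P-gp inducers (including: Carbamazepine, Phenytoin, Rifampicin", goes on to list seven drugs, and says that if they "need to be taken, they should be administered simultaneously with or after afatinib". A further sentence warns that strong inducers may reduce afatinib exposure and cites the sponsor's clinical summary.

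The section closes by asking investigators to judge the P-gp status of concomitant drugs themselves, because the lists may change.

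**The concern.** The cross-reference does not lead to the rule it announces. A reader who goes from Section 1.2 to Section 4.2.2.1 for the inhibitor rule finds a timing rule for the opposite class.

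Section 4.2.2.1 is the operative text. Exclusion criterion 11 (Section 3.3.3), the removal criteria (Section 3.3.4.1), the medication check before first dose (Section 6.2.1) and the mucositis guidance (Section 10.1.3) all send sites to Section 4.2.2 or 4.2.2.1. Section 1.2 is background.

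What is at stake is the dosing of individual patients. An inhibitor taken before afatinib may raise exposure. If that contributed to a drug-related event of Grade 3 or higher, Section 4.1.4.1 would require a pause and a dose reduction that cannot be reversed. The documents give no frequency for such a sequence. The sponsor would also have little chance of seeing the problem in the database, because the eCRF records concomitant medication only for rash and diarrhoea (Tables 6.2.1: 1, 6.2.2: 1 and 6.2.3: 1).

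**Working it through.** No statistical calculation is involved. The check compares the two sections and counts the drugs named. All text compared is current protocol text, not the amendment log.

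**1. The rules side by side**

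| | Section 1.2 | Section 4.2.2.1 |
|---|---|---|
| Inhibitors | Take simultaneously with afatinib | Caution about prior dosing; no instruction on when to take |
| Inducers | No timing rule | Take simultaneously with or after afatinib |

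**2. The data in Section 1.2**

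| Drug (class) | Timing relative to afatinib | Afatinib dose | Result |
|---|---|---|---|
| Ritonavir (inhibitor) | With, or 6 h after | 40 mg | No relevant change |
| Ritonavir (inhibitor) | 1 h before | Single 20 mg | AUC +48%, Cmax +39% |
| Rifampicin (inducer) | Pretreatment | 40 mg | AUC −34%, Cmax −22% |

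Ritonavir "did not relevantly change the exposure to 40 mg afatinib when taken simultaneously with or 6 h after afatinib". Those two favourable conditions, with and after, are the ones that the Section 4.2.2.1 timing sentence allows. For the inducer only pretreatment is reported, so nothing in the protocol corresponds to a rule of taking inducers with or after afatinib. This match is the reason for reading *inducers* as a slip. One caveat applies: in the ritonavir results dose and timing change together (40 mg against 20 mg), so they are not a clean comparison of timing alone.

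**3. The lists in Section 4.2.2.1**

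- Inhibitors named: 22, all distinct.
- Inducers named: 7.
- In both lists: 1 (ritonavir).
- Inhibitors with no timing instruction within that section: 22 − 1 = 21. Ritonavir has one only because it is also listed as an inducer.

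**4. Compatibility**

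Taking an inhibitor simultaneously with afatinib obeys Section 1.2 and avoids the prior dosing that Section 4.2.2.1 warns about. For ritonavir, simultaneous dosing meets both the inhibitor rule and the inducer rule. The sections are therefore inconsistent in which class carries the rule, but a site can comply with both.

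**The case against.** The strongest reply is that nothing is missing from the protocol as a whole. Section 1.2 states the inhibitor rule without limiting it to particular drugs, so all 22 named inhibitors are covered. The caution in Section 4.2.2.1 is itself about timing, since it names prior dosing as the hazard. The cross-reference is not empty either, because it leads to the inhibitor list and that caution. Section 1.2 also refers sites to the Investigator's Brochure and the label. If exposure did rise, the plan has a day-15 call about adverse events and dose reductions, visits every 28 days, and pauses and reductions driven by tolerability. All of this stands. It limits the weight of the point but does not explain why the operative section gives the rule to the other class.

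Three stronger readings are tempting, and the documents do not support them.

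- **That 21 inhibitors have no timing rule in this trial.** The count of 21 is true only of Section 4.2.2.1 read alone. It is the length of a list, not a measure of risk or of patients affected.
- **That the protocol permits inhibitor dosing shortly before the next afatinib dose.** Dosing is daily (Section 4.1.1: "Continuous daily dosing, one cycle consists of 28 days"), so an open-ended *after* would include 24 − 1 = 23 h after one dose, which is 1 h before the next. But the current text does not apply *or after* to inhibitors, apart from the doubly listed ritonavir, and the 1 h result comes from a single 20 mg dose. The arithmetic is only a reason not to copy *or after* into the inhibitor rule without an interval.
- **That the inducer timing advice is unsupported.** The protocol shows no data for it, but Section 4.2.2.1 cites the clinical summary in the adjoining sentence and Section 1.2 refers to the Investigator's Brochure. Neither was available, so this is a question for the sponsor, not a demonstrated fault.

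**Conclusion.** The inconsistency is real and lies in the section that sites are told to use. Section 1.2 gives the timing rule for inhibitors and points to Section 4.2.2.1; Section 4.2.2.1 gives it for inducers and leaves inhibitors with a caution. An inhibitor/inducer slip is the probable cause. That judgement rests on the match with the ritonavir data and on the protocol alone; the sponsor's clinical summary or Investigator's Brochure could show that the inducer wording was deliberate. Even then, the inhibitor rule announced in Section 1.2 would still be absent from Section 4.2.2.1.

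The practical risk is limited, and its size in patients cannot be derived from the documents. A reader might infer that the safety or efficacy results are compromised. Nothing in the documents shows that, and no effect on serious adverse events, drug-related adverse events or time to symptomatic progression is claimed. The point should be corrected because it is a safety-relevant dosing instruction and the correction is nearly free.

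**What to change.** In Section 4.2.2.1:

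1. State that P-gp inhibitors, if needed, are to be taken simultaneously with afatinib, in agreement with Section 1.2. Do not add an open-ended *or after*.
2. State that ritonavir, which is in both lists, follows the inhibitor rule.
3. Have the sponsor check against the clinical summary and the Investigator's Brochure whether *inducers* was intended in the timing sentence, and correct or confirm it accordingly.
4. Keep the warning that strong inducers may reduce afatinib exposure.

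The cost is one or two sentences, through an amendment or a letter to sites, after a check of two documents the sponsor already holds. No new data, visits or procedures are needed, and the SAP does not change.

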4.2.2.2 Restrictions on diet and life style

Patients should be advised to avoid any foods known to aggravate diarrhoea (see [Appendix 10.1.1](#)).

To prevent skin related adverse events it is recommended to avoid long exposure to sunlight and intense exposure to UV light and/or harsh detergents (pH5 neutral), see also [Appendix 10.1.2](#).

4.2.3 Contraception and pregnancy

Female patients must have a negative pregnancy test (β -HCG test in urine or serum) prior to commencing trial treatment.

Females will be considered to be of childbearing potential unless surgically sterilized by hysterectomy or bilateral tubal ligation/salpingectomy, or post-menopausal for at least two years. Women of childbearing potential who are sexually active and unwilling to be abstinent or to use an acceptable method of birth control during the trial and for at least 28 days after the end of active therapy are not allowed to participate in the trial.

Acceptable methods of contraception for females include abstinence, hormonal contraception and double barrier method. Double barrier method of contraception is defined as two barrier methods used simultaneously each time the patient has intercourse. Accepted barrier methods include diaphragm, female condom, cervical cap, male condom and Intrauterine Device (IUD) (the diaphragm and cervical cap must be used in conjunction with spermicidal jelly/cream). If hormonal contraceptives are used, at least one barrier method should also be used. Partner vasectomy, natural 'rhythm' and spermicidal jelly/cream are not acceptable as methods of contraception. Female patients who are not of childbearing potential due to being postmenopausal (2 years without menses) or surgical sterilization (oophorectomy, hysterectomy and/or tubal ligation) do not need to use contraception.

Male patients should use adequate contraception (e.g., condom and spermicidal jelly) during the trial and for at least 28 days after the end of active therapy.

If a woman becomes pregnant during the treatment period this must be reported as a drug exposure during pregnancy case, even if no event occurred. For cases of paternal exposure to

Proprietary confidential information.

© 2019 Boehringer Ingelheim International GmbH or one or more of its affiliated companies. All rights reserved.

This document may not - in full or in part - be passed on, reproduced, published or otherwise used without prior written permission.

the BI product during the trial, the pregnancy (mother is not a participant in the trial) has also to be reported to BI, if the father (participant in the trial) voluntarily reports it to the investigator.

In both cases the pregnant woman has to be followed up until birth of the baby; then it has to be reported whether the woman had a normal delivery or not and whether the newborn showed any pathological findings.

If pregnancy is associated with a SAE, both, SAE form and pregnancy monitoring form must be completed.

Table 4.2.3: 1 Pregnancy reporting

Timing of pregnancy	Action
Prior to commencing trial medication	Patient should be withdrawn from the trial immediately, as per exclusion criteria #7. No reporting necessary.
During trial treatment	
Treatment must be stopped immediately and the pregnancy should be reported to the sponsor immediately using the pregnancy monitoring form (Part A). If the investigator wishes to give any further treatment with trial medication, this must be discussed and agreed upon with the BI clinical monitor. If trial medication is continued despite pregnancy, a risk/benefit analysis should be documented.
 
The pregnancy should be followed up to final outcome and the outcome, including the health status of the newborn and/or any premature termination should be reported to the sponsor on the pregnancy monitoring form (Part B) (refer to Section 5.2.2.2).
 
If a pregnancy is accompanied by an SAE, an SAE form must also be completed. In addition, any event leading to the termination of pregnancy (i.e. spontaneous, accidental, or induced abortion; as well as miscarriage, intrauterine foetal demise/death) must be reported as an SAE.

End of Treatment (EOT) though Follow-up visit	
The pregnancy should be reported to the sponsor immediately using the pregnancy monitoring form (Part A).
 
The pregnancy should be followed up to final outcome and the outcome, including the health status of the newborn and/or any premature termination should be reported to the sponsor on the pregnancy monitoring form (Part B).
 
If a pregnancy is accompanied by an SAE, an SAE form must also be completed. In addition, any event leading to the termination of pregnancy (i.e. spontaneous, accidental, or induced abortion; as well as miscarriage, intrauterine foetal

Proprietary confidential information.

© 2019 Boehringer Ingelheim International GmbH or one or more of its affiliated companies. All rights reserved.

This document may not - in full or in part - be passed on, reproduced, published or otherwise used without prior written permission.

	demise/death) must be reported as an SAE.
--	---

4.3 TREATMENT COMPLIANCE

The trial medication will be given to the patient in accordance with the protocol and the instructions of the investigator. The appropriate number of afatinib tablets will be provided to the patient to be self-administered at home. Patients will be asked to return all unused trial medication at each visit. It is the investigator's or his delegate's responsibility to conduct compliance check at each of these returns. At the end of each visit, remaining medication will be collected. Discrepancies between the number of tablets remaining and the calculated number of tablets that patients should have taken will be documented and explained. If the patient is eligible for a further course of treatment, a new bottle will be dispensed.

Patients experiencing emesis should not take a replacement dose. Afatinib must not be taken more than once a day under any circumstances.

A maximum of 20% of the dispensed afatinib doses may be missed for other reasons aside from drug-related AEs or instructions from investigator. Patients who miss afatinib treatment more frequently are considered non-compliant. All overdoses are considered as non-compliance.

Proprietary confidential information.

© 2019 Boehringer Ingelheim International GmbH or one or more of its affiliated companies. All rights reserved.

This document may not - in full or in part - be passed on, reproduced, published or otherwise used without prior written permission.

5. VARIABLES AND THEIR ASSESSMENT

The primary endpoint of this study is the safety assessment; refer to [Section 5.2.1](#) for a description of safety endpoints.

5.1 EFFICACY

Efficacy assessments are secondary endpoints.

5.1.1 Endpoints of efficacy

Time to symptomatic progression (TTSP) is defined as the time from first administration of afatinib to the date of first documented clinically significant symptomatic progression that requires change in or stopping anti-cancer treatment according to investigator's assessment.

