3.3.4 Removal of patients from therapy or assessments

3.3.4.1 Removal of individual patients

The investigator or patient themselves may stop trial treatment at any time for safety or personal reasons.

If a patient is entered in violation of inclusion/exclusion criteria, the sponsor, in discussion with the investigator, will determine the medical risk/benefit on a patient-by-patient basis and can require such a patient be discontinued from the trial treatment.

The investigator or the sponsor may permanently discontinue a patient's participation at any time for any of the following reasons:

- patient withdraws consent, without the need to justify the decision
- patient fails to follow protocol requirements/directions and represent a safety issue for the patient
- eligibility criteria are violated and represent a safety issue for the patient
- patient requires concomitant medication which may interfere with the trial medication (see [Section 4.2.2](#))
- patient is no longer able to participate for other medical reasons (e.g., surgery, adverse events or other diseases)
- adverse events that cannot be managed by dose reduction
- further dose reductions considered necessary but not allowed according to the protocol (see [Section 4.1.4.1](#))

Proprietary confidential information.

© 2019 Boehringer Ingelheim International GmbH or one or more of its affiliated companies. All rights reserved.

This document may not - in full or in part - be passed on, reproduced, published or otherwise used without prior written permission.

- patient is found to be pregnant during trial participation (please refer to [Table 4.2.3: 1](#))
- is diagnosed with interstitial lung disease (ILD)
- change in patient's status creating an unfavourable risk/benefit in favour to stop trial treatment.
- termination of the trial
- Start of any other anti-cancer treatment

When discontinuation is due to a AE/SAE the investigator must follow the event until it is resolved, becomes chronic, or remains stable with no resolution expected. Data on these events must be collected in the electronic case report form (eCRF). For guidelines in the management of class expected adverse events, refer to [Appendix 10.1](#).

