5.1.2 Assessment of efficacy

Progression will be assessed by investigator. Lung cancer-related symptoms will be assessed by investigator at each visit. The date in which patient experiences progression requiring change in anti-cancer medication or stopping trial treatment will be defined as date of clinically significant symptomatic progression.

Although radiological assessments are not part of this study, the investigators will be allowed to perform imaging assessments at their discretion. Radiological progression may not occur at same time point as symptomatic progression. .

Proprietary confidential information.

© 2019 Boehringer Ingelheim International GmbH or one or more of its affiliated companies. All rights reserved.

This document may not - in full or in part - be passed on, reproduced, published or otherwise used without prior written permission.

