7.3.2 Secondary analyses

TTSP

TTSP is the time from the date of the first administration of afatinib to the date of first documented clinically significant symptomatic progression that requires stopping afatinib according to investigator's assessment.

TTSP [days] = date of last administration of trial drug - (date of start of treatment) + 1

Kaplan-Meier estimates and 95% confidence intervals for the 25th, median, and 75th percentiles of the survival distribution will be calculated for TTSP, using Greenwood's standard error estimate. Kaplan-Meier curves will be produced without confidence intervals.

Proprietary confidential information.

© 2019 Boehringer Ingelheim International GmbH or one or more of its affiliated companies. All rights reserved.

This document may not - in full or in part - be passed on, reproduced, published or otherwise used without prior written permission.

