##### **Time to symptomatic progression (TTSP)**

Defined as the time (number of days) from first administration of afatinib to the date of first documented clinically significant symptomatic progression that required stopping afatinib according to investigator's assessment.

Patients will be considered to have clinically significant symptomatic progression if the reason for termination of trial medication is recorded as 'progressive disease' or 'worsening or AE of underlying cancer disease', on the termination of trial medication eCRF page.

Therefore TTSP will be derived as:

$TTSP \text{ [days]} = \text{date of last administration of trial drug (where 'progressive disease' or 'worsening or AE of underlying cancer disease' selected on the termination of trial drug eCRF page)} - (\text{date of start of treatment}) + 1$

Kaplan-Meier estimates and 95% confidence intervals for the 25th, median, and 75th percentiles of the survival distribution will be calculated for TTSP. Greenwood's standard error estimate will be used. Kaplan-Meier curves will also be produced.

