##### *Censoring rules for TTSP:*

- For patients who have 'other AE', 'non-compliance with protocol', 'lost to follow-up', 'patient refusal to continue taking trial medication' or 'other' recorded on the termination of trial medication eCRF page, these patients will be censored at the date of last administration of the trial drug recorded on the termination of trial drug page;
- For patients who are still on treatment, these patients will be censored at cut-off date for interim analysis and at the date of EOT visit for final analysis.

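### TTSP is defined two ways, and a switch of therapy for symptomatic progression can be coded 'other' and censored when the event occurs

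*Protocol*

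**What the plan says.** **Event, wider wording.** Protocol 5.1.1 measures TTSP from first dose to the first documented "clinically significant symptomatic progression that requires change in or stopping anti-cancer treatment", in the investigator's judgement. Protocol 5.1.2 sets the date as the one on which the patient has "progression requiring change in anti-cancer medication or stopping trial treatment will be defined as date of clinically significant symptomatic progression". Protocol 5.4 likewise takes the date on which worsening symptoms call for a change of treatment.

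**Event, narrower wording.** Protocol 7.3.2 counts "clinically significant symptomatic progression that requires stopping afatinib" and computes TTSP as "date of last administration of trial drug - (date of start of treatment) + 1". SAP 7.5.2 follows it with "clinically significant symptomatic progression that required stopping afatinib". SAP section 4 describes this as a clarification of the definition.

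**Coding.** SAP 7.5.2 recognises the event by two entries on the termination page: progressive disease, and worsening or AE of the underlying cancer. For five other entries (other AE, non-compliance, loss to follow-up, patient refusal, other) it says "these patients will be censored at the date of last administration of the trial drug recorded on the termination of trial drug page".

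**Switches.** Protocol 3.3.4.1 lists "Start of any other anti-cancer treatment" among the reasons for discontinuing a patient. None of the seven entries named in SAP 7.5.2 corresponds to it.

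**The concern.** TTSP is the only efficacy criterion in the synopsis and the only efficacy endpoint in SAP 5.2.2. Two analysts, one working from Protocol 5.1.1 and one from SAP 7.5.2, could classify the same patient differently.

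The practical exposure is the switch. If symptoms progress and the site moves the patient to another therapy, the form can record the consequence (new treatment) instead of the cause (progression). The only home for that reason among the named entries is 'other', and the SAP then censors the patient at last dose. That censoring is informative, because it removes a true event at the time it happens. The SAP has no rule for looking behind an 'other' stop.

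**Working it through.** The documents give no TTSP estimate, event count or formal sample size (Protocol 7.6), so there is no planned figure to reproduce.

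**Step 1. Where the two definitions can part.**

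| Situation | Protocol 5.1.1 | SAP 7.5.2 |
|---|---|---|
| Afatinib stopped for symptomatic progression, coded as progressive disease | Event | Event |
| Switch for symptomatic progression, coded 'other' | Event | Censored at last dose |
| Stop for toxicity, symptomatic progression later (followed under Protocol 6.2.4) | Can be an event, if it requires a change of treatment | Already censored at last dose |
| Palliative radiotherapy for symptoms, afatinib resumed | Unclear: 5.1.1 says treatment, 5.1.2 says medication | No termination, so no event at that time |

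**Step 2. How a switch reaches 'other'.** Protocol 4.2.2.1 bars other systemic anti-cancer therapy alongside afatinib, apart from stated hormonal exceptions, so a switch normally ends afatinib and produces a termination entry. The current list in 3.3.4.1 names the start of other treatment but does not name progression itself. A site that carries that listed reason to the form finds no matching entry among the seven.

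**Step 3. Size for the affected mechanism.** Assume exponential TTSP with true median M, so the hazard is λ = ln 2 / M. If a share f of progression stops is coded 'other', regardless of time, the observed event hazard is λ(1 − f), and the observed median is ln 2 / [λ(1 − f)] = M/(1 − f). Take M = 12 months as an assumption:

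| f (assumed) | 12/(1 − f) | Simulated Kaplan-Meier median |
|---|---|---|
| 0 | 12.00 | 12.03 |
| 2% | 12.24 | 12.28 |
| 5% | 12.63 | 12.66 |
| 10% | 13.33 | 13.33 |
| 20% | 15.00 | 15.01 |

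The simulation used 200,000 patients and assumed non-progression stops at 15% of the progression hazard. The proportional increase does not depend on M: 1/0.95 = 1.053, 1/0.90 = 1.111, 1/0.80 = 1.25.

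**Step 4. An effect in the other direction.** The progressive-disease entry does not require symptoms, so a stop for imaging-only progression counts as an event. If 10% to 20% of such stops come on average 2 to 4 months before symptomatic progression (assumed), the simulated median falls from 12.03 to between 11.87 and 11.46. That is 0.16 to 0.57 months shorter.

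**The case against.** The best reply is that change and stopping nearly coincide here. Afatinib is the only trial treatment, other systemic anti-cancer therapy is essentially barred alongside it, and Protocol 5.4 describes afatinib continuing until symptoms require a change. The SAP follows Protocol 7.3.2 and declares its clarification. A switch for progression is a stop for progression, two event codes are available for it, and Table 6.2.3: 1 gives disease progression as an example of a stop reason. Other reasons in 3.3.4.1, such as pregnancy or ILD, also have no code of their own, and the form itself is not in the documents.

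Much of this stands, and it rules out four readings that a reader might infer:

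- **That the SAP departs from the protocol.** The protocol is inconsistent with itself; 7.3.2 is already narrow.
- **That switches for progression are lost as a rule.** They are lost only if coded 'other' or under another censored entry. This is a coding risk whose frequency is unknown.
- **That palliative radiotherapy for progression is a lost event.** Protocol 4.2.2.1 permits it as symptom control, and 5.1.2 speaks of medication. Where it did count, the event would usually be deferred to a later stop. If 5% to 20% of events were deferred by a mean of 2 to 4 months (assumed), the simulated median would be 12.13 to 12.87 against 12.03.
- **That reported TTSP is too long overall.** Imaging-only stops, and a last dose that precedes documented progression, both shorten it.

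The reply does not remove the conflicting definitions, or the absence of any check on 'other' stops.

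**Conclusion.** The point holds as an inconsistency of definition plus a coding risk. Protocol 5.1.1, 5.1.2 and 5.4 define the event by a required change in or stopping of treatment. Protocol 7.3.2 and SAP 7.5.2 define it by stopping afatinib, and a switch for symptomatic progression entered as 'other' is censored when the event occurs.

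For those patients TTSP is overstated. At an assumed 12-month median, a 2% to 10% share adds about 0.2 to 1.3 months and a 20% share adds 3.0. These figures rest on a constant hazard, miscoding unrelated to time, and shares that the documents do not supply. The net direction across all coding effects is unknown.

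TTSP is a descriptive secondary endpoint in a single-arm trial without hypothesis tests, so the primary SAE endpoint and any error rate are untouched. The change is worth making because it is cheap and TTSP is the trial's only efficacy result under SAP 5.2.2.

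**What to change.** 1. Use one event definition in Protocol 5.1.1, 5.1.2, 7.3.2 and SAP 7.5.2, and bring 5.4 into line. State in it whether palliative radiotherapy with afatinib resumed counts as an event. No new eCRF item is needed.
2. Before database lock, list every 'other' stop. Review each against the recorded reason and the new anti-cancer medication and date on the follow-up form (Table 6.2.4: 1). Count as events those where symptomatic progression led to the switch. Write the reclassification rule before opening the listing. The follow-up item covers therapy taken since the EOT visit, so a switch made before EOT must be found from the recorded reason.
3. Report TTSP by Kaplan-Meier with and without the reclassified events, as one sensitivity run.

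**Cost.** Some wording, a short listing review and one further run of existing code. TTSP may come out slightly shorter than under the present rule.
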